12.0 Study Device Details

12.1 List the medical devices or in vitro diagnostics to be studied or used and attach any FDA or sponsor correspondence relating to the device to the application in the Study Documents section:

(Note: Device category descriptions added to the Help link December, 2014)

View Details Device Name App	Is this a new device or a new use of an already	IDE Number
------------------------------	---	------------

				approved device	
	Option Elite IVC FIlter		Yes	No	
Manufact	turer/Supplier of Device	Argor	1		
Medicare	Category	A	В		
Where w	ill the Devices Be Stored				
Will Devi	ces be supplied at no Cost	No			
Is this a	HUD (HDE)	No			
HDE Nun	nber				
Is the De	evice FDA Approved	Yes			
	new device or a new use eady approved device	No			
Is an IDE	necessary	No			
IDE Num	ber				
Who hold	ds the IDE	N/A			
IDE Deta	nils				
	oinion of the sponsor, e level of risk associated device	No Si	gnificant Risk		
⊟	Denali IVC Filter		Yes	No	
Manufact	turer/Supplier of Device	Bard			
Medicare	Category	ПА	В		
Where w	ill the Devices Be Stored	Inter	ventional Radiology		
Will Devi	ces be supplied at no Cost	No			
Is this a	HUD (HDE)	No			
HDE Nun	nber				
Is the De	evice FDA Approved	Yes			
	new device or a new use eady approved device	No			
Is an IDE	necessary	No			
IDE Num	ber				
Who hold	ds the IDE	N/A			
IDE Deta	ils				
	oinion of the sponsor, e level of risk associated device	No Si	gnificant Risk		

13.0 Other Approvals and Registrations

13.1 * Do any study activities take place on patient care units:

⊙ Yes ○ No

If **Yes**, attach a letter of support for the study from the involved patient care manager(s).

13.2 * Does your protocol involve any radiation exposure to patients/subjects? The UCSF Radiation

Safety Committee requires review of your protocol if it includes administration of radiation as standard of care \underline{OR} research exposures:	part of
⊙ Yes C No	
* This study may generate genetic data that may be broadly shared (e.g. submitted to NIH for Genome-Wide Association Studies (GWAS) in dbGaP, TCGA, etc):	
C Yes O No	
13.4 * This study involves administration of vaccines produced using recombinant DNA technologie human subjects:	s to
C Yes O No	
* This study involves human gene transfer (NOTE: Requires NIH Recombinant DNA Advisory Committee (RAC) review prior to CHR approval):	
C Yes ⊙ No	
13.6 This study involves other regulated materials and requires approval and/or authorization from following regulatory committees:	n the
☐ Institutional Biological Safety Committee (IBC)	
Specify BUA #:	
☐ Institutional Animal Care and Use Committee (IACUC)	
Specify IACUC #:	
▼ Radiation Safety Committee	
Specify RUA #:	
Radioactive Drug Research Committee (RDRC)	
Specify RDRC #:	
Controlled Substances	

14.0 Procedures

14.1 * Procedures/Methods (Help Text updated 9/13) For clinical research list all study procedures, test and treatments required for this study, including when and how often they will be performed. If there are no clinical procedures, describe the Methods:

This is a prospective, randomized trial comparing two FDA-approved inferior vena cava filters, the Denali retrievable IVC filter (Bard Peripheral Vascular Inc., Tempe, AZ) and the Option Elite (Argon Medical, Athens, Texas).

Patients scheduled for IVC filter placement at UCSF Department of Interventional Radiology (IR) will be asked by the IR physician performing the procedure at either UCSF Mt. Zion, Moffitt Bay or Moffitt hospital if they wish to participate in this observational study. Recruitment will be conducted by the physicians

performing the IR procedures only. No additional recruitment calls, emails, posters or web pages are necessary. All procedures and the randomization to one of the two experimental groups will be carefully explained before obtaining signed written consent.

Screening:

Screening will be conducted by the IR physician prior to the placement of the IVC filters. Since this is a standard of care study, patients who are recommended for IVC filter placement and are scheduled for the procedure are generally eligible.

The screening procedures are part of routine care before IVC filter placement and would be done even if patients did not join the study.

The study doctor will review the results of most recent routine care imaging scans (CT or MRI) of the abdomen and pelvis. This is done to confirm that the diameter of IVC is no wider than 2.8cm. Both filters are FDA-approved to be placed in an IVC with maximal diameter of 2.8cm.

The study doctor will also review ultrasound of the lower extremity, when available, to confirm that a blood clot was in fact present prior to performing the study. This ensures that patients who present for IVC filter placement are screened properly.

The following screening procedures should be done within 12 days before the IVC filter placement procedure as part of the standard of care.

- A complete physical exam
- \cdot $\,$ The study doctor will ask about medical history and how well patient is able to do daily activities
- · Routine care blood tests (about 2 tablespoons)
 - o This is to ensure that the INR and platelet count of the patient is within the safe limits to perform an invasive procedure.

After Enrollment:

If the screening procedures show that the patient is eligible and consents to take part in the study, IVC filter placement will occur after randomization.

After enrollment, the following procedures will be done during the study: Just as with screening, all of these procedures are part of regular IVC filter placement care.

Randomization:

Randomization will occur on the day of procedure or prior clinic visit with IR physician to either the Denali or Option IVC filter. All IR attending physicians on the protocol are familiar with placement of either filter type. Prior to opening study to accrual, 75 sealed security envelopes with the word Denali printed on a card inside and 75 sealed security envelopes with the word Option will be assembled by IR staff not involved in the research. The envelopes will be mixed up and placed in a bag. Computerized randomization programs and tables were considered but we feel the envelopes will work best as there may be limited time after patient is consented and procedure begins. This is especially true as some filters are placed emergently. Previous IR studies have used this randomization technique with great success.

Filter Placement:

Placement of an IVC filter involves the insertion of a plastic tube (catheter) into a vein in the neck. Some numbing medicine (Lidocaine) will be injected in the skin over the vein before the catheter is inserted. Intravenous medications will be given to induce moderate sedation (Fentanyl for analgesic and Versed for moderate sedation). Once the catheter has been placed into the vein, it will be advanced into the IVC. Once in correct position, x-ray contrast material (x-ray dye-Omnipage 350) will be injected through the catheter and x-ray pictures taken. A series of x-ray pictures will be obtained of the IVC. These pictures are taken as part of standard of care to determine the position of the renal veins with respect to the IVC. The top of the filter must sit below the renal veins so it doesn't cause obstruction of the renal veins. In addition, pictures of the IVC are taken to serve as another tool in measuring the diameter of the IVC to make sure the diameter of the IVC is less than 2.8cm. This is particularly important in situations when a CT or MRI of the abdomen and pelvis is not available to have reviewed prior to the procedure. Once pictures are obtained and it is made certain that the IVC diameter is less than 2.8cm, the filter will be inserted through the catheter, and placed below the renal veins. During the placement procedure, positioning of the filter will be monitored with x-ray pictures. At the completion of the procedure the catheter will be removed and pressure will be applied to the insertion site until the bleeding has stopped. All of this is part of routine standard of care for placement of the filter. The doctor performing the procedure will be asked to complete a short questionnaire after IVC filter placement which will be attached to "Study Documents".

Follow-Up:

After the IVC filter placement procedure patient status will be followed by the interventional radiology doctors.

Per standard of care after IVC filter placement, patient will be monitored in the hospital for up to 1 hour after the procedure. If patient is in stable condition and sedation has resolved, they will return home the same day or returned to their hospital rooms.

A tentative appointment for follow up and filter retrieval will be ordered by IR physician at time of filter placement in APEX. This will ensure that scheduling and study staff will be aware that further patient and primary care follow-up is required.

Patient primary care physician and/or relevant medical staff will be telephoned one month after IVC filter placement to determine if patient is medically stable and suitable for IVC filter removal.

If IR and other doctors agree that IVC filter removal is recommended, patient will be scheduled to return for follow-up imaging and filter retrieval. If patient is not medically stable or still at high risk for blood clots, we will attempt to schedule a follow up one month later. Close contact with primary physician and patient will be maintained to ensure that filter is removed as soon as possible. APEX scheduling will be used to make sure follow up is performed at regular intervals.

At follow-up appointment these routine tests per standard of care before IVC filter removal will be performed:

- A physical exam
- · The study doctor will ask about medical history, how well patient is able to do daily activities, and if they are experiencing any possible symptoms related to the IVC filter placement such as abdominal or back pain.
- A rotation CT focused to the site of the filter will be performed as part of routine practice of filter removal. This is done to ensure the filter has not migrated or that the filter has not penetrated through the walls of the IVC such that filter retrieval would be unsafe.
- · IR physician will determine if patient status is stable and safe for IVC filter removal. If not, physician will discuss with primary care doctor if filter needs to remain permanently in patient or if later retrieval should be considered at subsequent follow up visits.
- · IVC filter retrieval will be performed under moderate sedation. This procedure is very similar in nature to the filter placement procedure. The IVC filter is removed via a similar process to the way in which it was placed. X-ray dye (contrast) will be injected around the filter to assure that the filter and the area beneath the filter are free of blood clots and that it is safe to proceed with removal. A catheter-based snare will be used to engage the hook at the end of the filter and the filter will then be enveloped by a removal sheath and removed from the body.

Imaging Analysis:

Single blind CT and x-ray imaging analysis will be conducted by a trained radiologist doctor using standard imaging tools and workstations (Agfa PACS V.6). The radiologist will be unaware which patient received which filter type to minimize any potential bias in searching for IVC filter complications. The radiologist will be instructed to look for the following complications of the IVC filter per Society of

Filter penetration as defined by more then 3mm penetration of IVC wall by one or more

- components of the IVC filter
 - o Also look for signs that other organs or spine were penetrated
- Filter tilt as defined by greater than 15 degrees tilt perpendicular to axis of IVC
- Filter migration as defined by more than 1 cm from initial filter location
- Filter thrombus as defined by clot formed in filter mesh
- Filter fracture as defined by breakage of one or more of filter components

Statistics will be compiled and analysis will be performed by statistician using SPSS software.

Statistical and Power Analysis

Interventional Radiation (SIR) guidelines:

IVC filter penetration (defined as greater than 3mm) through the IVC wall be the primary complication we will be measuring.

For sample size, we determined that with \sim 75 patients per group and similar differences in incidence or penetration as our preliminary study (25) (22% & 10%) we will see a significant difference at the p = 0.05 level with power 80%. If the difference is a little wider (25% vs. 10%) we will see significance at 50 patients per group. This calculation is using a comparison of proportions test with a z-statistic.

A correlation test will be performed as well as a survival analysis where a failure is penetration. This would give two curves from time of insertion to time of CT scan showing penetration. The log rank statistic would look at comparisons over time.

Finally, we will also do an analysis of struts counting penetration as one or more and use the total number of penetrating struts as a secondary analysis.	
If you have a procedure table, attach it to the submission with your other study documents.	
14.2 Interviews, questionnaires, and/or surveys will be administered or focus groups will be condu	ıcted:
⊙ Yes C No	
List any standard instruments used for this study:	
Questionnaire given to IR docs after filter placement	
Attach any non-standard instruments at the end of the application.	
14.3 Conduct of study procedures or tests off-site by non-UCSF personnel:	
C Yes O No	
If yes, explain:	
14.4 Sharing of experimental research test results with subjects or their care providers:	
C Yes ⊙ No	
If yes, explain:	
14.5 * Specimen collection for future research and/or specimen repository/bank administration:	
C Yes O No	
14.6 Time commitment (per visit and in total):	
The total time commitment per subject would be the same as for any standard of care IVC filter patient. No additional study visits outside of IVC filter placement, retrieval and imaging are necessary. There may be brief follow up telephone calls by IR reception staff and research coordinators which will be minimal and only done for follow up and continuity of care.	
14.7 Locations:	
UCSF Moffitt hospital, Mission Bay or Mt. Zion hospital department of interventional radiology.	
14.8 Describe the resources in place to conduct this study in a way that assures protection of the ri and welfare of participants:	ghts
UCSF medical staff nurses, physicians and administrative staff involved in the standard of care procedures for patients already scheduled for IVC filter placement. 6 or greater interventional radiology physicians will also be on protocol and our trained extensively in IVC filter placement and monitoring. An independent radiologist will also be on key study staff to assist with the unbiased imaging analysis.	

In addition there is a dedicated clinical research coordinator that will facilitate patient care and contact, primary physician contact, data collection and IR staff coordination.

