The purpose of the present study is to characterize the incidence, time-course, and magnitude of complications of two commonly used IVC filters. Patients who present to Interventional Radiology for IVC filter will be randomized to have either a Denali filter or an Option filter placed. Patients will then be contacted 30-days following filter placement to come for filter removal. If it is not clinically safe for a patient to have the filter removed after 30 days, other attempts will be made to schedule for filter removal at 30-day intervals until the filter is removed. The filter placement and filter removal will be performed in the usual fashion according to the standards of our current practice. Upon filter removal, note will be made to potential complications including: filter perforation, filter migration, filter fracture and thrombus within the filter. Another main purpose of the study is to try to increase the numbers of patients who return promptly for filter removal. Many patients continue to have IVC filters in place for far longer than is needed due to poor follow up procedures and lack of tracking due to many patients being referred in from other services.

Little is presently known regarding the complication tendency of the relatively new Denali conical retrievable IVC filter (Cook, Bloomington, Indiana). The Option has been researched more and has been found to have a slightly lower incidence of complications than other conical filters.

In a prospective multicenter study of 100 Option filters, investigators noted one case of penetration among 39 filters assessed during retrieval cavograms (12); however, penetration was not dealt with as a dedicated endpoint. The option studies also did not randomize what filter was used and the data was only examined retrospectively with varying timepoints. The Denali was approved under an FDA "similar device" exemption so has not been subject to systematic long term study. The present study aims to characterize the incidence and time course of penetration and other complications at regular intervals for the Option filter compared with the Denali.

9.2 Preliminary studies:

The department of interventional radiology at UCSF has recently conducted retrospective comparative studies of IVC filter complications, comparing two devices in two separate studies. This research has inspired us to propose a randomized prospective trial to more clearly evaluate the efficacy of two newer IVC filters.

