10.0 Sample Size and Eligibility	
10.1 Number of subjects that will be enrolled at UCSF and affiliated institutions:	
150	
10.2 Total number of subjects that will be enrolled at all sites (Help Text updated 9/13):	
150	
10.3 Estimated number of people that you will need to consent and screen here (but not necessaril enroll) to get the needed subjects:	у
300	
10.4 Explain how and why the number of subjects was chosen (Help Text updated 9/13):	
The numbers are based on statistical power analysis and examination of our findings from previous IVC filter retrospective studies done by UCSF interventional radiology. The most recent study showed that one group of filters had 22% penetration and the other had 10% penetration. However, because the numbers in each group were too small, no significant difference in degree of penetration was found. For sample size, we determined that with \sim 75 patients per group and similar differences in incidence or penetration as our preliminary study (25) (22% & 10%) we will see a significant difference at the p = 0.05 level with power 80%. If the difference is a little wider (25% vs. 10%) we will see significance at 50 patients per group. This calculation is using a comparison of proportions test with a z-statistic.	
To make sure this will be feasible, we looked at the total number of IVC filters placed in the previous year at UCSF Mount Zion and UCSF Parnassus. In 2013, 169 IVC filters were placed in patients between the two hospitals. Since this is a standard of care study and no extra time committment will be required, we expect most patients will be consented and agree to be followed in the study. Over a two year proposed study timeline with on average 340 patients receiving IVC filters, we expect to consent about 300 patients in order to get the 100-150 needed to find significant findings. We expect half of the 300 consented patients to be lost to follow up and not return for follow up imaging and retrieval.	
10.5 * Eligible age range(s):	
 □ 0-6 years □ 7-12 years □ 13-17 years ☑ 18+ years 	

1. Patients scheduled for IVC filter placement at UCSF Moffitt, Mount Zion, or Mission Bay Interventional Radiology Service. 2. 18+ 1. Necessity of permanent IVC filter
Necessity of permanent IVC filter
1. Necessity of permanent IVC filter
2. Genetic or physical abnormalities of the inferior vena cava

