16.0 Risks and Benefits

16.1 * Risks and discomforts:

Risk of IVC Filter Placement and Removal (Standard of Care)

- -Insertion site hematoma
- -Filter migration
- -Filter fracture and fragment embolization
- -Penetration of the vena cava by the filter legs
- -Recurrent PE
- -Vena cava thrombosis
- -Allergic reaction to iodinated contrast agent
- -Inability to remove IVC filter
- -Loss of privacy due to inadvertent loss of data disclosure

16.2 Steps taken to minimize risks to subjects:

Filter removal and filter placement will be conducted by a skilled M.D. Interventional Radiologist at UCSF Mission Bay, Mt. Zion, or Moffitt hospital. All MD IR staff are extensively trained in the placement and removal of IVC filters. The primary investigator will ensure the proper training of any physician placing filters on study. Patient data will be stored in APEX per standard of care or on a secured and approved UCSF database.

PI [name] MD

UCSF IRB: 14-13307	CT02201277	22 of 32
All patients included in the trial will be contacted to ur the complications associated with long-term filter dwe	. ,	
16.3 Benefits to subjects:		
• Yes • No If yes, describe: The main benefit to subjects is that they will be follow contacting them at regular intervals to ensure filter is the patient. Many IVC filter patients are not contacted for complications from the filter that also increase with	removed as soon as it is determined to be safe for for follow up retrieval and are at much greater risk	
16.4 Benefits to society:		
The benefit to society and the medical community is to of IVC filter complications and their time course. An ac standard of care for IVC filter patients and ensure the as soon as it is safe to do so.	dditional benefit is that we are trying to improve the	
16.5 Explain why the risks to subjects are reaso	nable:	
The risks to the subject are reasonable since these are having a filter placed whether or not they agreed to participate discovered during the course of the study showing the necessary in order to provide further safety data on both	articipate in the study. There may be additional risks t one device may be safer than the other. This is	

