17.0 Data and Safety Monitoring Plan

17.1 Describe the plan for monitoring data and safety (Help Text updated 9/13):

DATA SAFETY MONITORING

Because this is a standard of care observational prospective study on two FDA approved and commonly used devices, our data and safety monitoring plan will primarily consist of the standard monitoring of patients during and after any clinical procedure conducted by interventional radiology.

come up during the study with either device, we will notify IRB as required and consider modifying the

ADVERSE EVENTS

study.

During the study, site personnel will note any change in the condition(s) and the occurrence and nature of any adverse events. For 30 days after removal of IVC filter, patients will be followed for any adverse event that could be related to the IVC filter or removal.

FOLLOW-UP OF PATIENTS AFTER ADVERSE EVENTS

Investigator Follow-Up:

The investigator should follow all unresolved adverse events if attributed to the IVC filter device until the event has resolved to baseline grade or better, the event is assessed as stable by the investigator, new therapy is initiated, the patient is lost to follow-up, or the patient withdraws consent. Every effort should be made to follow all serious adverse events considered to be related to trial-related procedures until a final outcome can be reported.

During the study period, resolution of adverse events (with dates) should be documented on the Adverse Event CRF and in the patient's medical record to facilitate source data verification (SDV). If, after followup, return to baseline status or stabilization cannot be established, an explanation should be recorded on the Adverse Event CRF.

DATA REVIEW

Investigators will conduct continuous review of data from UCSF enrolled patient safety at monthly research study group or site committee meetings where the results of each patient's treatment are discussed. The discussion will include the number of patients, complications as described in the protocol, and observed responses.

WITHDRAWAL

Discontinuation of Patients:

The investigator will discontinue patients from the study in the following circumstances:

- Patient is not a candidate for IVC filter retrieval to do continuing embolism risk or declining overall health status
- The patient or attending physician requests withdrawal of the patient from the study.

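### The procedures date one follow-up call, to the patient's doctor and about removal only, and no contact is specified to collect outcomes or adverse events from patients who do not return

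*Combined protocol and SAP*

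**What the plan says.** The follow-up text in 7.1 and 14.1 is the same. Its one dated contact is a call: "Patient primary care physician and/or relevant medical staff will be telephoned one month after IVC filter placement to determine if patient is medically stable". The question put is whether the filter can come out, and the patient is booked for imaging and retrieval if the doctors agree. If the patient is not ready, follow-up is attempted a month later. A tentative appointment is also ordered at placement, and there is an undated promise: "Close contact with primary physician and patient will be maintained to ensure that filter is removed as soon as possible".

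Section 9.1 describes a different first contact: "Patients will then be contacted 30-days following filter placement to come for filter removal". Where removal is not yet safe, "other attempts will be made to schedule for filter removal at 30-day intervals until the filter is removed".

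Section 16.2, under steps to reduce risk, says "All patients included in the trial will be contacted" (the rest of that sentence is damaged in the public copy, and nothing here relies on it). Section 16.3 gives as the main benefit to subjects that staff will be "contacting them at regular intervals to ensure filter is" removed once that is safe. Section 14.6 says only that brief calls may be made, for follow-up and continuity of care.

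On expected losses, section 10.4 says: "We expect half of the 300 consented patients to be lost to follow up and not return for follow up imaging and retrieval".

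On safety, section 17.1 says "our data and safety monitoring plan will primarily consist of the standard monitoring of patients during and after any clinical procedure". Site staff also note adverse events during the study, and patients are followed for related events for 30 days after the filter is removed.

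**The concern.** There are two problems. The first is a conflict. The sections that staff will work from send the dated call to a third party, while the background and the risk-benefit sections say the patient is contacted. Section 9.1 attributes poor follow-up partly to patients being referred in from other services, and the dated call goes largely through that same route.

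The second matters more for the analysis. No contact, to doctor or patient, is assigned any outcome or adverse-event question. If half the patients do not come back, what is known about recurrent embolism, other events, death or scans done elsewhere will come mainly from those who did. Non-return is unlikely to be unrelated to health: section 17.1 itself discontinues patients who are not retrieval candidates because of continuing embolism risk or declining health. The planned log-rank comparison of time to penetration also treats non-returners as censored, and judging whether that censoring is informative needs vital status and the reason for not returning.

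**Working it through.** **Step 1. Contacts side by side.**

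| Section | Who is reached | When | Purpose | Outcome or adverse-event items |
|---|---|---|---|---|
| 7.1, 14.1, call | Doctor or other medical staff | One month | Stability, suitability for removal | None listed |
| 7.1, 14.1, close contact | Doctor and patient | Undated | Prompt removal | None listed |
| 9.1 | Patient | 30 days, then attempts every 30 days | Scheduling removal | None listed |
| 14.6 | Not stated | Undated, optional | Follow-up, continuity of care | None listed |
| 16.2, 16.3 | All patients | Regular intervals, undated | Removal when safe (16.3) | None listed |

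**Step 2. What exists for a patient who never returns.**

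- Physician questionnaire (aim 3) and placement x-rays: yes, both are obtained at placement.
- CT for penetration, examination, symptom questions: none scheduled. All three belong to the return appointment.
- Adverse events: general noting during the study applies, but no route to the patient is described. The dated window runs from removal, so it never opens for a filter left in.
- Medical records: a listed source in 18.3, with no scheduled review described.
- Reason for leaving: recorded for withdrawals where it is known. Simple non-return is not addressed unless it is handled as noncompliance, which is a ground for discontinuation.

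**Step 3. Size of the group.** The plan's own figure first: 300 × (1 − 0.5) = 150, and in reverse 150 / (1 − 0.5) = 300, so the loss arithmetic in 10.4 is consistent. The envelopes, however, cover 75 + 75 = 150 patients. There are two readings:

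- A: 300 randomised and half lost, giving 150 non-returners and 150 imaged (75 per arm).
- B: 150 randomised and half lost, giving 75 non-returners and 75 imaged (37.5 per arm on average).

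**Step 4. Events at stake.** The documents give no adverse-event rate. Assume a proportion p, equal in returners and non-returners, of 5% with a range of 3% to 10%. Expected events = N × p in all patients and (N/2) × p in non-returners.

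| p | Reading A: all / non-returners | Reading B: all / non-returners |
|---|---|---|
| 3% | 9 / 4.5 | 4.5 / 2.25 |
| 5% | 15 / 7.5 | 7.5 / 3.75 |
| 10% | 30 / 15 | 15 / 7.5 |

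These are events with no specified inquiry. They are not events certain to be missed, because some would surface in records. If sicker patients return less often, the non-returners' share exceeds half.

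**Step 5. How far missing data could move a comparison.** With a fraction m of outcomes unknown in each arm and a proportion p among those seen, the arm's true proportion lies between p(1 − m) and p(1 − m) + m. With m = 0.5 and the protocol's 22% and 10% penetration rates:

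- 22% arm: 0.11 to 0.61.
- 10% arm: 0.05 to 0.55.
- Difference: 0.11 − 0.55 = −0.44 to 0.61 − 0.05 = +0.56.

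The range is 100 percentage points wide. Its width is 2m whatever the observed rates, so it applies equally to any yes/no safety outcome unknown in half of each arm. It is an outer limit, not a forecast. It shows that only a smaller m narrows what can be said. A call reduces m for safety outcomes. For penetration it helps only if it locates a CT done elsewhere.

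**The case against.** The strongest reply is that the documents already plan patient contact. Sections 14.1 and 9.1 can be read as one sequence: ask the doctor at one month, then call the patient in. A tentative appointment is ordered at placement, the scheduling system prompts regular follow-up, and 14.8 names a coordinator for patient contact, physician contact and data collection. Section 14.1 says the interventional radiology doctors follow the patient's status, and 17.1 adds monthly review of patients' results.

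Much of this stands, and it rules out stronger statements that a reader might infer:

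- That non-returners have no dated contact. Section 9.1 dates one at 30 days and repeats it. The defect is that 14.1 does not carry it over and that it serves only to schedule removal.
- That non-returners yield no outcome data, or only the observation of up to an hour after placement. The questionnaire, placement x-rays, adverse-event noting and medical records say otherwise.
- That return for CT hangs entirely on a third party answering. The tentative appointment and the promised patient contact are separate routes.
- That direct calls would raise the return rate, and with it precision. The documents give no basis for any such gain, and the expected 50% loss may already allow for patient contact.

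What the reply does not supply is a question about events or outcomes, put to or about a patient who stays away, at a stated time.

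**Conclusion.** The point holds in a limited form and should be fixed. Sections 7.1 and 14.1 do not carry out the dated patient contact in 9.1 or the contact with all patients promised in 16.2-16.3. Across all sections, no call is specified to collect outcomes or adverse events. By the protocol's own expectation this leaves half of the patients, 75 or 150 depending on the reading of 10.4, with no scheduled primary-outcome imaging and no specified safety inquiry. The device safety comparison therefore rests mainly on returners. About half of all events would fall in the uninquired group if event rates were equal, and more if ill patients return less. The event counts rest on an assumed 3% to 10% rate; the finding does not. The documents do not support the reading that nothing at all is known about non-returners.

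**What to change.** Reconcile the follow-up text in 7.1 and 14.1 with 9.1 and 16.2-16.3, so that one schedule states who is contacted and when.

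At the 30-day contacts already planned, have the coordinator named in 14.8 also reach the patient or surrogate and complete a one-page form for every randomised patient. It records:

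- alive or dead, with date;
- filter in or out;
- recurrent PE or DVT;
- other adverse events;
- any CT done elsewhere, so that it can be obtained for the blinded read;
- the reason for not returning.

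Continue until removal, death, withdrawal of consent or a stated end of study follow-up; without that last limit the calls have no end for filters never removed. The 30 days of adverse-event follow-up after removal stay as written. Section 17.1 should make clear that patients discontinued as non-candidates for retrieval stay on the form, and 14.6 should allow calls that collect data. Decisions on removal stay with the clinicians as written.

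The cost is a few minutes of coordinator time per contact and one form. Under 150 randomised that is at most 150 forms at day 30, and fewer at each later interval as filters come out. No extra visit or imaging is needed. The form will not measure penetration.
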